11.2 Analysis

Population: FAS and PPS populations

Stratification: Table: NA

Listing: By subject

Statistics:

Baseline and Demographic variables will be summarized and listed. Overall summaries will include descriptive statistics for continuous measures (N=sample size, n=number of subjects with respective parameter, mean, median, maximum, minimum, interquartile range (IQR), standard deviation and frequency of missing values) and for categorical measures (N=sample size, frequency, percent, frequency of missing values).

12. Exposure to IMP

12.1 Variables and derivations

In eCRF exposure form we are capturing the treatment dosing related data and the dates of first IMP administration will be derived as the first date of dosing from the Exposure form in eCRF. The date of last IMP administration will be derived as the date of last dose of IMP from the End of the Study form in eCRF page.

Note: Total amount of missed dose on 3 consecutive or 15 days in total within the 6 months' time frame is considered as per standard definition per sponsor, the same definition has beens used in all previous insulin studies.

The following variables will be listed for exposure to IMP:

- Subject Number
- Date of treatment administration
- Total amount of dose consumed
- Number of missed doses
- Duration of exposure(days)

The duration of exposure, which will be derived as follows:

Duration of exposure (days) =
 (Date of last IMP administration - Date of first IMP administration) + 1

12.2 Analysis

| Population: | FAS and PPS populations |
|-----------------|---|
| Stratification: | Table: NA |
| | Listing: By Subject |
| Statistics: | Listing will be provided for daily dosing treatment exposure data for |
| | each subject. |

13. IMP compliance

13.1 Variables and derivations

The compliance to IMP will be calculated based on information obtained from the exposure form in eCRF at each visit (i.e. for treatment period) as per mentioned in protocol section 7.6.

Compliance will be derived and reported by visit (i.e. for treatment period) and overall as follows:

For visit:

- Compliant" if, the response to the question "Were there any missed doses" is answered "No" or, if the answered is "Yes" and the response to the question "Did the subject miss more than 3 consecutive days of study medication" is answered as "No".
- "Not Compliant" if, the response to the question "Were there any missed doses" is answered "Yes" and, the response to the question "If yes, indicate the number of missed doses" is equal or more than 3,
- "Unknown" otherwise

For overall

- "Compliant" if, the response to the question "Were there any missed doses" is answered "No" or, if the answered is "Yes" and the response to the question "Did the subject miss more than 3 consecutive days of study medication" is answered as "No" or the total of all missed doses in the treatment period is less than equal to 15.
- "Not Compliant"
 - if, the response to the question "Were there any missed doses" is answered "Yes" and, the response to the question "If yes, indicate the number of missed doses" is equal or more than 3 and,
 - The response of the question "Did the subject miss more than 3 consecutive days of study medication" is answered "Yes" then if the total of all missed doses in the treatment period is more than 15.

• "Unknown" otherwise.

The following mentioned parameters will be summarised in table:

IMP compliance categories by each visit and overall

The following variables will be provided in the listing:

- Subject Number
- Visit
- Start date of study drug administration
- Date of dose on last day prior to visit
- Compliance status

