## 7.6. Treatment Compliance

Subject compliance with study medication will be assessed at each visit of the treatment period. Compliance will be assessed by

- subject's glycemic control
- adherence to the visit schedule
- dosing-titration algorithm
- administration of study insulin, and
- any other parameters the investigator deems necessary.

Deviations from the prescribed dosage regimen should be recorded in the eCRF.

The subject will be considered significantly noncompliant if during the study he or she misses

- more than 3 consecutive days of study medication (full doses), or
- more than 15 cumulative days of study medication (full doses).

Similarly, a subject will be considered significantly noncompliant if he or she is judged by the investigator to have intentionally or repeatedly taken more than the prescribed amount of medication. All such subjects will be considered to have withdrawn from the study. The last observation carried forward (LOCF) replacement of these subjects will be taken under the supervision of Lilly or its designee if the target number of subjects (a minimum of 200) is at risk to be achieved.

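### SAP 13.1 calls a subject Compliant overall when either missed-dose limit is respected, whereas protocol 7.6 makes a breach of either limit noncompliance; its by-visit categories also overlap

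*SAP*

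**What the plan says.** **Protocol 7.6 (Treatment Compliance)** joins two missed-dose limits with *or*. A subject is significantly noncompliant after missing "more than 3 consecutive days of study medication (full doses), or" "more than 15 cumulative days of study medication (full doses". It adds a third ground, that the investigator judges the subject to have "intentionally or repeatedly taken more than the prescribed amount of medication". The stated consequence is: "All such subjects will be considered to have withdrawn from the study".

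**SAP 12.1 (Exposure)** describes the sponsor's standard definition, also with *or*: "Total amount of missed dose on 3 consecutive or 15 days in total".

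**SAP 13.1 (IMP compliance)** says compliance is derived "as per mentioned in protocol section 7.6". Its rules, in short:

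- *Overall Compliant*: no missed doses; or missed doses with the question on a run of more than 3 days answered No; "or the total of all missed doses in the treatment period is less than equal to 15".
- *Overall Not Compliant*: missed doses, 3 or more of them, and the run question answered Yes, "then if the total of all missed doses in the treatment period is more than 15".
- *By visit, Compliant*: no missed doses, or missed doses with the run question answered No.
- *By visit, Not Compliant*: missed doses, with a count of 3 or more in any pattern.
- *Unknown*: anything else, at both levels.

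SAP 13.2 reports these categories by visit for the FAS and PPS, in a table and a listing. SAP 13.1 also asks for the overall category.

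**The concern.** The overall rule has the protocol's logic the wrong way round. In the protocol, either breach is enough to fail. In SAP 13.1, respecting either limit is enough to pass. The SAP presents this as an implementation of protocol 7.6, not as a change of definition, and its own section 12.1 still uses *or*.

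In a study of self-administered, self-titrated insulin with hypoglycemia as the primary endpoint, readers use the compliance table to judge whether the observed risk reflects real exposure. An overall row that misses one-limit breaches gives too favourable a picture. It could also conflict with the disposition table: a subject recorded on the End of Study form as discontinued for noncompliance could appear as Compliant overall.

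The by-visit fault is different in kind. The two categories are not complements, so two programmers could code the same visit differently and both be following the text.

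**Working it through.** The plan gives no figure for this point, so there is none to reproduce. The check compares the rules as logic.

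**Inputs.** Let R be the longest run of missed days and T the total missed. Dosing is once daily (protocol 7.1), so a missed dose counts as a missed day. The treatment period is 24 weeks = 168 days, and a visit interval is nominally 28 days (SAP Table 7.1).

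**Rules.**

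- Protocol 7.6, missed-dose part: noncompliant if R > 3 **or** T > 15.
- SAP 13.1 overall Compliant: T = 0, or R ≤ 3, **or** T ≤ 15.
- SAP 13.1 overall Not Compliant: T ≥ 3 **and** R > 3 **and** T > 15.
- SAP 13.1 by visit: Compliant if T = 0 or R ≤ 3; Not Compliant if T ≥ 3 (R and T within the interval).

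The overall Compliant sentence mixes *and* with *or* and can be grouped in two ways: the 15-dose clause can stand alone, or apply only where doses were missed. Both groupings give the same status for every case.

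**Overall status, test cases.**

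| R | T | Protocol 7.6 | SAP 13.1 overall |
|---|---|---|---|
| 3 | 3 | not noncompliant | Compliant |
| 4 | 4 | noncompliant | Compliant |
| 10 | 10 | noncompliant | Compliant |
| 15 | 15 | noncompliant | Compliant |
| 1 | 16 | noncompliant | Compliant |
| 3 | 20 | noncompliant | Compliant |
| 1 | 40 | noncompliant | Compliant |
| 4 | 16 | noncompliant | Not Compliant |
| 20 | 20 | noncompliant | Not Compliant |

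The subject with 40 scattered misses has missed 40/168 = 23.8% of treatment days.

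**All feasible (R, T) pairs over 168 days.** The discordant pairs are exactly those that breach one limit:

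- R > 3 with T ≤ 15: for T = 4 to 15 there are T − 3 values of R, so 1 + 2 + … + 12 = 78 pairs.
- R ≤ 3 with T > 15: for R = 1, T = 16 to 84 (69 pairs); for R = 2, T = 16 to 112 (97); for R = 3, T = 16 to 126 (111). Sum 277.
- Together 78 + 277 = 355 pairs are noncompliant by the protocol and Compliant by the SAP. No pair errs in the other direction.

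These counts show the logic. They are not expected numbers of subjects.

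**By-visit status over 28 days.** The overlap is R ≤ 3 with T ≥ 3: for R = 1, T = 3 to 14 (12 pairs); for R = 2, T = 3 to 19 (17); for R = 3, T = 3 to 21 (19). That gives 48 pairs in both categories. Any run over 3 days means at least 4 missed doses, so it falls only under Not Compliant. The same 10-day run within one interval is thus Not Compliant for its visit and Compliant overall.

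**How many subjects?** The documents give no missed-dose distribution. As an assumption only, 10,000 simulated subjects were run for each of six patterns, set by the daily chance of a miss after a taken dose and after a missed dose.

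| After taken | After missed | Noncompliant by protocol | Of all subjects: noncompliant but SAP Compliant |
|---|---|---|---|
| 2% | 2% | 0.0% | 0.0% |
| 5% | 5% | 1.0% | 1.0% |
| 10% | 10% | 62.9% | 61.6% |
| 2% | 50% | 32.4% | 29.3% |
| 5% | 50% | 67.4% | 28.0% |
| 1% | 70% | 42.9% | 37.8% |

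The size therefore depends entirely on the pattern of missed doses.

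**The case against.** The strongest reply is that this is a descriptive status with little reach, and most of that reply stands.

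*Per-protocol set and completers.* Because protocol 7.6 treats noncompliant subjects as withdrawn, a reader might infer that the faulty rule alters PPS membership and the number of completers. The documents do not support this. SAP 6.3 programs the PPS from FAS membership, a completion or discontinuation date not before Visit 8, and the absence of a major deviation. Its text criterion for time off drug is a separate one, more than 14 consecutive days. SAP 10.1 takes trial completion from the End of Study form, treatment completion from the last-dose date, and the discontinuation reason from the form. None of these reads the 13.1 status. The protocol's withdrawal rule could still affect the PPS through a recorded discontinuation or a major deviation, but that route bypasses 13.1.

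*By-visit direction.* A reader might also infer that the overlap inflates compliance. It need not. If the overlapping visits were coded Not Compliant, compliance by visit would look lower, and three scattered misses do not in themselves breach the protocol. By visit the status is undefined, not overstated.

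*Visibility.* A long run is not hidden from the report altogether, because the visit in which it falls is Not Compliant.

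None of this rescues the overall rule. It contradicts the section it cites, under either grouping of its sentence.

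**Conclusion.** The point holds for the compliance table and listing. Every subject who breaches exactly one missed-dose limit is Compliant overall under SAP 13.1 and noncompliant under protocol 7.6, and the overall row can err only towards overstatement. Separately, a visit with 3 or more missed doses and no run over 3 days has no defined status, and the cut-off of 3 doses matches neither protocol limit.

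Two smaller mismatches belong with this. SAP 12.1 names 3 and 15 days where the protocol says more than 3 and more than 15. SAP 13.1 also leaves out the overuse criterion, so a subject judged to overuse can be Compliant.

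The primary hypoglycemia estimate in the FAS is unaffected. The conclusion assumes that one missed dose is one missed day and that the questions are answered. The number of subjects affected cannot be derived from the documents. This should be corrected before the compliance output is programmed, but it does not threaten the trial's main result.

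**What to change.** In SAP 13.1:

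- **Overall.** Not Compliant if the run question is Yes at any visit **or** total missed doses exceed 15. Compliant only if both criteria can be answered and neither is met. Unknown if neither limit is known to be breached and answers are missing. Unknown must stay, because a plain otherwise-Compliant rule would turn missing data into compliance.
- **By visit.** Use the run question alone: Yes is Not Compliant, No or no missed doses is Compliant, missing is Unknown. Delete the rule based on 3 or more missed doses.
- **Overuse.** Carry over the protocol's third criterion and name its data source. The documents show no eCRF item for this judgement, though protocol 7.6 requires deviations from the dosage regimen to be recorded. If no source exists, state that the status covers missed doses only.

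In SAP 12.1, reconcile the thresholds with the protocol's wording so that protocol 7.6, SAP 12.1 and SAP 13.1 state one rule.

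**Cost.** The missed-dose changes use eCRF questions that 13.1 already names, so they need SAP wording and code only. The overuse item costs the same if a record exists, and otherwise a sentence on the limitation.

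### SAP 13.1 reverses the logic of protocol 7.6, so a subject who breaks only one missed-dose limit is tabulated as compliant overall, and its by-visit labels overlap

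*SAP*

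**What the plan says.** Protocol 7.6 (Treatment Compliance) gives two missed-dose limits joined by *or*: more than 3 consecutive days, or "more than 15 cumulative days of study medication (full doses"). It adds a third ground, investigator judgement that the subject has "intentionally or repeatedly taken more than the prescribed amount of medication". It then states: "All such subjects will be considered to have withdrawn from the study".

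SAP 13.1 (IMP compliance) says compliance is derived as set out in protocol 7.6 and announces no departure.

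- **Overall, *Compliant*:** no missed doses, or missed doses with the question on more than 3 consecutive days answered No, "or the total of all missed doses in the treatment period is less than equal to 15".
- **Overall, *Not Compliant*:** the number of missed doses "is equal or more than 3" and, where the consecutive-days question is answered Yes, "then if the total of all missed doses in the treatment period is more than 15". The two bullets are joined by *and*.
- **By visit, *Compliant*:** no missed doses, or missed doses with the consecutive-days question answered No.
- **By visit, *Not Compliant*:** any missed doses whose number "is equal or more than 3". They need not be consecutive.

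The over-use ground does not appear in SAP 13.1. The note in SAP 12.1, described there as the sponsor's standard definition, also uses *or*: "Total amount of missed dose on 3 consecutive or 15 days in total". Its thresholds are 3 and 15, where protocol 7.6 has more than 3 and more than 15.

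**The concern.** If noncompliance means breaking one limit or the other, compliance must mean keeping both. SAP 13.1 overall does the opposite: keeping either limit is enough to be *Compliant*, and both must be broken to be *Not Compliant*. A subject who breaks exactly one limit gets the wrong overall label.

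The by-visit rule has a different fault. Its two labels rest on different quantities, the longest run for one and the number of missed doses for the other, so both can be true at once. The label printed would then depend on the order of the program's statements.

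At stake is the compliance table planned in SAP 13.2 for the full analysis set (FAS) and the PPS. It gives context for a single-arm hypoglycaemia incidence and should describe compliance as the protocol defines it.

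**Working it through.** The documents state no compliance rate, so there is no planned figure to reproduce. The check is a logical comparison.

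**Notation.** T = total missed days; R = longest run of missed days. The treatment period has 24 × 7 = 168 planned daily doses, and a nominal visit interval has 28. The questionnaire answers are taken to be complete and correct, and the overall consecutive-days answer is taken as Yes if it is Yes at any visit (SAP 13.1 does not say how visits combine).

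**Overall rule.** Let A be R > 3 and B be T > 15.

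- Protocol 7.6, missed-dose grounds: noncompliant = A or B, so compliant = (not A) and (not B).
- SAP 13.1: *Compliant* = (T = 0) or (not A) or (not B). *Not Compliant* = (T ≥ 3) and A and B, which reduces to A and B because T > 15 implies T ≥ 3.

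The *Compliant* sentence can be bracketed in two ways, with the total-of-15 clause standing alone or inside the missed-doses branch. Both give the same result: *Compliant* is the exact complement of (A and B). The SAP and the protocol therefore disagree whenever exactly one of A and B holds, and agree otherwise.

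| Pattern | T | R | Protocol 7.6 | SAP 13.1 overall |
|---|---|---|---|---|
| one 4-day gap | 4 | 4 | noncompliant | Compliant |
| one 10-day gap | 10 | 10 | noncompliant | Compliant |
| one 15-day gap | 15 | 15 | noncompliant | Compliant |
| 20 scattered days, runs of at most 2 | 20 | 2 | noncompliant | Compliant |
| 30 days, runs of at most 3 | 30 | 3 | noncompliant | Compliant |
| 16 days including a run of 4 | 16 | 4 | noncompliant | Not Compliant |

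A pair (T, R) fits in D days if T + ceil(T/R) − 1 ≤ D. The disagreeing pairs for D = 168 are:

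- A only (T from 4 to 15, R from 4 to T): 1 + 2 + … + 12 = 78.
- B only: R = 1 with T from 16 to 84 gives 69; R = 2 with T from 16 to 112 gives 97; R = 3 with T from 16 to 126 gives 111. The sum is 277.
- Total: 78 + 277 = 355.

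This counts patterns, not expected subjects.

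**By-visit rule.** *Compliant* = (T = 0) or (R ≤ 3). *Not Compliant* = T ≥ 3. Both hold whenever T ≥ 3 and R ≤ 3. For D = 28:

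- R = 1, T from 3 to 14: 12.
- R = 2, T from 3 to 19: 17.
- R = 3, T from 3 to 21: 19.
- Total: 12 + 17 + 19 = 48 patterns carrying both labels.

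The simplest is 3 isolated missed doses (T = 3, R = 1), which breaks neither limit in 7.6. If that is resolved as *Not Compliant*, the by-visit rule is stricter than the protocol. No pattern is left without a label.

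**By visit against overall.** A gap of 4 to 15 days inside one interval has R > 3 and T ≥ 3, so that visit is *Not Compliant* only. If the study total stays at 15 or fewer, the overall label is *Compliant*. The same table then contradicts itself.

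**After correction.** With overall *Not Compliant* = A or B, the SAP and the missed-dose grounds of 7.6 agree on every feasible pattern. With by-visit *Not Compliant* = R > 3, the overlap falls from 48 patterns to 0.

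**The case against.** The best reply is that little depends on this label. The primary analysis in SAP 19.2.1 does not use it, and PPS membership under SAP 6.3 has its own criteria. SAP 12.1 and 12.2 list missed doses and daily dosing by subject, so the raw information survives. The by-visit rows still flag a gap of 4 to 15 days within one interval, and the by-visit rule can be stricter than 7.6. All of this stands. It limits the point to a reporting fault and means that only the overall row is shown to understate noncompliance.

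Extreme patterns should not be used to enlarge the point. Alternate-day dosing throughout (84 of 168 missed) would be *Compliant* overall, but only if the subject stayed in the study long after passing the limits in 7.6. Nor does it help that a 15-day gap is *Compliant* overall yet fails PPS criterion (c), which allows no more than 14 consecutive days off drug. The protocol itself sets different limits for the two purposes.

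A reader might also infer from the withdrawal sentence in 7.6 that noncompliant subjects leave the study, lose hypoglycaemia follow-up and so bias the primary incidence downward. The documents do not establish this. The sentence may be only a classification: protocol 8.1.1 and 8.2 do not name noncompliance, and PPS criterion (c) would be almost redundant after criterion (b) if a gap of more than 3 days meant exit. SAP 10.1 does list noncompliance with study drug as a discontinuation reason, so some exits may occur. For those, protocol 5.1.1, 8.1.1, 8.2 and 9.1.1 already provide safety follow-up and hypoglycaemia collection to Visit 9 or the early termination visit. No noncompliance rate is given, so any size put on such a bias would rest on assumed exit rates.

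**Conclusion.** Wrong as written, and minor. SAP 13.1 claims to apply protocol 7.6 but labels a subject who breaks exactly one missed-dose limit as *Compliant* overall. Its by-visit labels both apply when 3 or more doses are missed with no run longer than 3 days. It also omits the over-use ground.

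The logical result rests only on the two texts and complete questionnaire answers. The number of subjects affected is unknown. The effect is confined to the compliance table and listing: the overall row understates noncompliance as 7.6 defines it, while the by-visit rows are ambiguous and may overstate it. It would be wrong to conclude that the whole table errs in one direction, that the primary incidence changes, or that PPS membership changes.

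**What to change.** In SAP 13.1, overall:

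- *Not Compliant*: more than 3 consecutive missed days at any treatment-period visit, **or** more than 15 cumulative missed days, **or**, where recorded, investigator-judged intentional or repeated over-use.
- *Compliant*: none of these.
- *Unknown*: cannot be determined.

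In SAP 13.1, by visit: replace the criterion of 3 or more missed doses with the consecutive-days question answered Yes, so that the labels are mutually exclusive.

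In SAP 12.1: align the note to more than 3 consecutive or more than 15 in total.

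The cost is a small SAP and program edit. Over-use would be read from the deviation or eCRF record. No protocol amendment is needed. If the protocol is amended for another reason, a cross-reference in 7.6 to the follow-up rules in 8.2 and 9.1.1 would remove doubt about the withdrawal sentence.

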13.2 Analysis

| Population: | FAS and PPS | |
|-----------------|---|--|
| Stratification: | : Table: By visit | |
| | Listing: By subject and visit | |
| Statistics: | The treatment compliance will be summarised (frequency | |
| | and percentages) for table and the listing will be presented. | |

14. Medical and treatment history

14.1 Variables and derivations

Medical history will be coded using the MedDRA central coding dictionary Version (refer to DMP for dictionary version).

Partial date imputation is not done for Medical and treatment history.

The following parameters will be summarised for the subject's Medical history as mentioned in eCRF:

- Number of subjects with at least one medical history
- Number of subjects for each medical history by SOC and PT

The following variables will be listed:

- Subject number
- System organ class/ Preferred terms / Reported terms
- Severity of medical history
- Start date of medical history
- End date of medical history

14.2 Analysis

| Population: | FAS and PPS | |
|-----------------|--|--|
| Stratification: | Table: By Primary SOC and PT in decreasing order Listing: By subject | |
| Statistics: | Medical and treatment history will be summarised (frequency and percentages) for table and listing also be provided. | |

15. Concomitant and other medications

